5 BIOSPECIMEN COLLECTION

5.1 Collection of Research (Immunologic) Blood Samples (all patients)

The amount of blood that may be drawn from adult patients (i.e., those persons 18 years of age or older) for research purposes shall not exceed 10.5 mL/kg or 550 mL, whichever is smaller, over any eight week period.

5.1.1 Immunologic Parameters (every 3 weeks unless not logistically feasible)

- Leukocyte CD3, CD4, CD8 subsets; CD4:CD8 ratio will be drawn at baseline and at each visit when on treatment (prior to vaccine) and then at follow-up visit while the patient remains on trial
- Additional studies will include but are not limited to quantitative and qualitative assessments of regulatory T-cells, Natural Killers cells, and Myeloid Derived Suppressor Cells.
- Assessment of serum levels of cytokines.
- Immunologic studies will be repeated more frequently if clinically indicated, and any abnormalities potentially related to treatment will be followed until they have resolved, or have been determined not to be treatment-related.
- Peripheral blood mononuclear cells (PBMC):
Intracellular cytokine staining assays for specific antigens may be done based on preliminary data.
- Phenotypic and functional analysis of immune cell subsets by flow cytometry.

5.1.1.1 Collection of Specimens

6 (10mL) green top sodium heparin tubes for PBMC; 2 (8mL) SST tubes for serum sample.

5.1.2 Natural Killer (NK) CELLS

The number and phenotype of NK cells will be determined by phenotypic analysis of PMBCs stained for CD56, CD3, CD8, and CD16 by flow cytometry.

5.1.3 Immune Subsets

Subsets of immune cells will also be followed in response to treatment.

5.1.4 Regulatory T Cells

Regulatory T cells have been shown to inhibit the activation and function of T cells that participate in antigen-specific immune responses. Higher levels of regulatory T-cells have been reported in the peripheral blood mononuclear cells of patients with several types of tumors. The number and phenotype of regulatory T-cells in peripheral blood mononuclear cells from patients in this study will be determined by 7-color flow cytometry analysis. Cells will be resuspended in staining buffer (phosphate-buffered saline containing 3% fetal bovine serum) and stained for CD4, CD25, CD127, FoxP3, CTLA-4, CD45RA, and CD8. The ratios between regulatory T-cells and CD4 effector cells and the ratios between regulatory T-cells and CD8 Effector cells will also be analyzed.

5.1.5 Additional Assays

Blood samples may be used for additional research studies, which may include one of the following - phenotypic and functional analysis of immune-cell subsets and analyses for cytokines (IFN- γ , IL-10, IL-12, IL-2, IL-4, etc.), chemokines, antibodies related to the tumor or vaccine, tumor associated antigens related to the tumor or the vaccine, and/or other immune response markers.

5.1.6 Biopsy analysis by interventional radiology (Optional).

When logistically feasible, pre-treatment and post-treatment samples may be obtained from consenting patients. Potential analysis could include PD1/PDL1 expression and immune cell infiltration.

5.1.7 Immunohistochemistry

The Laboratory of Pathology and the Warren G. Magnuson Clinical Center will perform Immunohistochemistry on biopsied tissue, if the patient elects to have the procedure. Immunohistochemistry of these tissue specimens will be obtained for CD4, CD8, and FOX-P3. In addition, phenotypic analysis of infiltrating immune cells will be performed.

Immunohistologic grading schema of the lesions

Score	%positive cells of each subtype
0	0
1	1-25%
2	26-50%
3	>50%

All staining will be categorized as being membrane or nuclear

5.2 Sample Storage, Tracking and Disposition

Samples will be ordered in CRIS and tracked through a Clinical Trial Data Management system. Should a CRIS screen not be available, the CRIS downtime procedures will be followed. Samples will not be sent outside NIH without IRB notification and an executed MTA.

5.2.1 Procedures for storage of tissue specimens in the Laboratory of Pathology

Tissues designated for clinical diagnostics are transported to the Laboratory of Pathology (LP) where they are examined grossly and relevant portions are fixed, embedded in paraffin and sectioned and stained for diagnostic interpretation. Unutilized excess tissues are stored for up to three months, in accordance with College of American Pathologists/Joint Commission on Accreditation of Healthcare Organizations (CAP/JCAHO) guidelines, and then discarded.

Following completion of the diagnostic workup, the slides and tissue blocks are stored indefinitely in the LP's clinical archives. All specimens are catalogued and retrieved utilizing the clinical laboratory information systems, in accordance with CAP/JCAHO regulations. The use of any stored specimens for research purposes is only allowed when the appropriate IRB approval has been obtained. In some cases, this approval has been obtained via the original protocol on which the patient was enrolled.

5.2.2 Blood Processing Core - Storage

All samples sent to the Blood Processing Core (BPC) will be barcoded, with data entered and stored in the LABrador (aka LabSamples) utilized by the BPC. This is a secure program, with access to LABrador limited to defined [name] lab personnel, who are issued individual user accounts. Installation of LABrador is limited to computers specified by [name]. These computers all have a password restricted login screen. All [name] lab personnel with access to patient information annually complete the NIH online Protection of Human Subjects course.

LABrador creates a unique barcode ID for every sample and sample box, which cannot be traced back to patients without LABrador access. The data recorded for each sample includes the patient ID, name, trial name/protocol number, time drawn, cycle time point, dose, material type, as well as box and freezer location. Patient demographics associated with the clinical center patient number are provided in the system. For each sample, there are notes associated with the processing method (delay in sample processing, storage conditions on the ward, etc.).

Barcoded samples are stored in barcoded boxes in a locked freezer at either -20 or -80°C according to stability requirements. These freezers are located onsite in the BPC and offsite at NCI Frederick Central Repository Services (American Type Culture Collection (ATCC)) in Frederick, MD. Visitors to the laboratory are required to be accompanied by laboratory staff at all times.

Access to stored clinical samples is restricted. Samples will be stored until requested by a researcher named on the protocol. All requests are monitored and tracked in LABrador. All researchers are required to sign a form stating that the samples are only to be used for research purposes associated with this trial (as per the IRB approved protocol) and that any unused samples must be returned to the BPC. It is the responsibility of the NCI Principal Investigator to ensure that the samples requested are being used in a manner consistent with IRB approval.

Following completion of this study, samples will remain in storage as detailed above. Access to these samples will only be granted following IRB approval of an additional protocol, granting the rights to use the material.

If, at any time, a patient withdraws from the study and does not wish for their existing samples to be utilized, the individual must provide a written request. Following receipt of this request, the samples will be destroyed (or returned to the patient, if so requested), and reported as such to the IRB. Any samples lost (in transit or by a researcher) or destroyed due to unknown sample integrity (i.e. broken freezer allows for extensive sample thawing, etc.) will be reported as such to the IRB.

Sample barcodes are linked to patient demographics and limited clinical information. This information will only be provided to investigators listed on this protocol, via registered use of the LABrador. It is critical that the sample remains linked to patient information such as race, age, dates of diagnosis and death, and histological information about the tumor, in order to correlate genotype with these variables.

5.2.3 Samples Sent to Clinical Services Program (CSP)

The samples will be processed through:

Clinical Services Program
NCI Frederick Cancer Research and Development Center
[name]
[name]
[contact]

On days samples are drawn, [name] at CSP should be notified (phone: [name]; fax [name]). She will arrange same-day courier delivery of the specimens.

The research samples will contain labels on the blood tubes that have the patient's initials, date of birth, the assigned protocol, and the date the sample was drawn. The transmittal forms accompanying the samples also contain the same information.

Once a patient's treatment schedule has been determined, it should be faxed to [name] at the Laboratory of Tumor Immunology and Biology/ NIH (Fax: [name]; phone: [name]) for planning purposes.

All data associated with patient samples are protected by a secure database. All samples drawn at the NIH Clinical Center will be transported to the NCI Frederick Central Repository by Leidos couriers.

Samples will be tracked and managed by the Central Repository database. All samples will be stored in liquid nitrogen. These freezers are located at NCI Frederick Central Repository in Frederick, Maryland.

American Type Culture Collection (ATCC) manages the NCI-Frederick Central Repositories under subcontract to Leidos Biomedical Research, Inc. NCI-Frederick Central Repositories store, among other things, biological specimens in support of NIH clinical studies. All specimens are stored in secure, limited access facilities with sufficient security, back up and emergency support capability and monitoring to ensure long-term integrity of the specimens for research.

ATCC's role is limited to clinical research databases and repositories containing patient specimens. ATCC does not conduct nor has any vested interest in research on human subjects, but does provide services and support the efforts of its customers, many of which are involved in research on human subjects.

It is the intent and purpose of ATCC to accept only de-identified samples and sample information. To the limit of our ability, every effort will be made to ensure that protected information is not sent electronically or by hard copy or on vial labels.

Sample data is stored in the BioSpecimen Inventory System II (BSI). This inventory tracking system is used to manage the storage and retrieval of specimens as well as maintain specimen data. BSI is designed for controlled, concurrent access. It provides a real-time, multi-user environment for tracking millions of specimens. The system controls how and in what order database updates and searches are performed. This control prevents deadlocks and race conditions. For security, BSI has user password access, three types of user access levels, and 36 user permissions (levels of access) that can be set to control access to the system functions. BSI provides audit tracking for processes that are done to specimens including shipping, returning to inventory, aliquoting, thawing, additives, and other processes. BSI tracks the ancestry of specimens as they are aliquoted, as well as discrepancies and discrepancy resolution for specimens received by the repository. If a specimen goes out of the inventory, the system maintains data associated with the withdraw request. Vials are labeled with a unique BSI ID which is printed in both eye readable and bar coded format. No patient specific information is encoded in this ID.

Investigators are granted view, input and withdraw authority only for their specimens. They may not view specimen data or access specimens for which they have not been authorized. Access to specimen storage is confined to repository staff. Visitors to the repositories are escorted by repository staff at all times.

5.2.4 Protocol Completion/Sample Destruction

Once primary research objectives for the protocol are achieved, intramural researchers can request access to remaining samples, provided they have an IRB-approved protocol and patient consent.

Samples and associated data will be stored permanently unless the patient withdraws consent. If the patient withdraws consent the participant's data will be excluded from future distributions, but data that have already been distributed for approved research use will not be able to be retrieved. The PI will report destroyed samples to the IRB if samples become unsalvageable or destroyed by environmental conditions (ex. broken freezer or lack of dry ice in shipping container) or if a patient chooses to withdraw his/her consent. Samples will also be reported as lost if they are lost in transit or misplaced by a researcher. Freezer problems, lost samples or other problems associated with samples will also be reported to the IRB, the NCI Clinical Director, and the office of the CCR, NCI.

6 DATA COLLECTION AND EVALUATION

6.1 Data Collection

The PI will be responsible for overseeing entry of data into an in-house password protected electronic system (C3D) and ensuring data accuracy, consistency and timeliness. The principal investigator, associate investigators/research nurses and/or a contracted data manager will assist with the data management efforts. All data obtained during the conduct of the protocol will be kept in secure network drives or in approved alternative sites that comply with NIH security standards. Primary and final analyzed data will have identifiers so that research data can be attributed to an individual human subject participant.

Clinical data will be entered in a secure electronic database, NCI C3D database, and hard copies will be stored in locked, secured areas. Completed eligibility checklists (developed by Central Registration Office, CRO), patient information/registration forms, and blood sample flow sheets will also be stored. Copies of all records of adverse events will be kept in the regulatory binder.

Complete records must be maintained on each patient, including the hospital chart with any supplementary information obtained from outside laboratories, radiology reports, or physician's records. These records will serve as the primary source material that forms the basis for the research record. All relevant data will also be entered in a computer database from which formal analyses will be done.

The primary source documentation will include: on-study information, including patient eligibility data and patient history; flow sheets, records of adverse events, specialty forms for pathology, radiation, or surgery; and off-study summary sheets, including a final assessment by the treating physician.

All adverse events, including clinically significant abnormal findings on laboratory evaluations, regardless of severity, will be followed until return to baseline or stabilization of event. Patients will be followed for adverse events for at least 30 days after removal from study treatment or until off-study, whichever comes first.

An abnormal laboratory value will be recorded in the database as an AE **only** if the laboratory abnormality is characterized by any of the following:

- Results in discontinuation from the study
- Is associated with clinical signs or symptoms
- Requires treatment or any other therapeutic intervention
- Is associated with death or another serious adverse event, including hospitalization.
- Is judged by the Investigator to be of significant clinical impact
- If any abnormal laboratory result is considered clinically significant, the investigator will provide details about the action taken with respect to the test drug and about the patient's outcome.

End of study procedures: Data will be stored according to HHS, FDA regulations, and NIH Intramural Records Retention Schedule as applicable.

Loss or destruction of data: Should we become aware that a major breach in our plan to protect subject confidentiality and trial data has occurred, the IRB will be notified.

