3.3.1 Dose Modifications

Adverse events (both non-serious and serious) associated with pembrolizumab exposure may represent an immunologic etiology. These adverse events may occur shortly after the first dose or several months after the last dose of treatment. Pembrolizumab must be withheld for drug-related toxicities and severe or life-threatening AEs as per **Table 4** below. See Section 4 for supportive care guidelines, including use of corticosteroids.

Table 4. Dose Modification Guidelines for Drug-Related Adverse Events

Toxicity	Hold Treatment For Grade	Timing for Restarting Treatment	Treatment Discontinuation
Diarrhea/Colitis	2-3	Toxicity resolves to Grade 0-1	Toxicity does not resolve within 12 weeks of last dose or inability to reduce corticosteroid to 10 mg or less of prednisone or equivalent per day within 12 weeks
	4	Permanently discontinue	Permanently discontinue
AST, ALT, or Increased Bilirubin	2	Toxicity resolves to Grade 0-1	Toxicity does not resolve within 12 weeks of last dose
	3-4	Permanently discontinue (see exception below) ^a	Permanently discontinue
Type 1 diabetes mellitus (if new onset) or Hyperglycemia	T1DM or 3-4	Hold pembrolizumab for new onset Type 1 diabetes mellitus or Grade 3-4 hyperglycemia associated with evidence of beta cell failure	Resume pembrolizumab when patients are clinically and metabolically stable
Hypophysitis	2-4	Toxicity resolves to Grade 0-1. Therapy with pembrolizumab can be continued while endocrine replacement therapy is instituted	Toxicity does not resolve within 12 weeks of last dose or inability to reduce corticosteroid to 10 mg or less of prednisone or equivalent per day within 12 weeks

Toxicity	Hold Treatment For Grade	Timing for Restarting Treatment	Treatment Discontinuation
Hyperthyroidism	3	Toxicity resolves to Grade 0-1	Toxicity does not resolve within 12 weeks of last dose or inability to reduce corticosteroid to 10 mg or less of prednisone or equivalent per day within 12 weeks
	4	Permanently discontinue	Permanently discontinue
Hypothyroidism		Therapy with pembrolizumab can be continued while thyroid replacement therapy is instituted	Therapy with pembrolizumab can be continued while thyroid replacement therapy is instituted
Infusion Reaction	2 ^b	Toxicity resolves to Grade 0-1	Permanently discontinue if toxicity develops despite adequate premedication
	3-4	Permanently discontinue	Permanently discontinue

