3.4 Study Calendar

Procedure	Screening/ Baseline ⁵	Treatment Cycles (21 days +/- 7 days) ¹								Cycle 9 and beyond	Post Treatment ⁶	
		C1 D1	C2 D1	C3 D1	C4 D1	C5 D1	C6 D1	C7 D1	C8 D1			
History and PE	X ²	X	X	X	X	X	X	X	X	X	X	X
Vital signs	X ²	X	X	X	X	X	X	X	X	X	X	X
Performance Score	X ²											
Height/Weight	X ³											
HIV, Hep B, C	X											
Pregnancy Test (Urine or Serum beta-HCG)	X ²											
UA ⁴	X ²											
PT/INR and PTT	X ²											
Chemistries ⁷	X ²	X	X	X	X	X	X	X	X	X	X	X
CBC	X ²	X	X	X	X	X	X	X	X	X	X	X
TSH	X ²			X	X	X	X	X	X	X	X	X
T/B/NK subsets	X ²	X	X	X	X	X	X	X	X	X	X	X
Tumor Markers: Calcitonin and CEA	X ²	X	X	X	X	X	X	X	X	X	X	X
Correlative Research Studies (research bloods see Appendix B)	X	continue at 3 month intervals									X ⁸	
Radiological Assessments (MRI or CT Neck, Ch/Abd/Pelvis, Bone Scan) ³	X	continue at 3 month intervals										
EKG ³	X	continue at 3 month intervals									X	
Biopsy (optional) ⁸												
Adverse Events		X										
Concomitant Medications		X										

¹ If patient is delayed, subsequent infusion must be at least 18 days later

Abbreviated Title: Pembrolizumab in MTC

Version Date: 3/26/18

² Must be done within 10 days prior to initiation of study therapy

³ Must be done within 8 weeks prior to initiation of study therapy, and then will be done every 3 months while patients remain on study

⁴ May be omitted if patient is incontinent and cannot provide a urine sample

⁵ Baseline/Screening requirements may also be used for Day 1 requirements if logistically necessary

⁶ Post-Therapy Assessment done 3 weeks after last treatment when logistically feasible (with a possible extension to 4 weeks if logistically necessary). Patients will be offered enrollment in the 04-C-0274 "Follow-Up Study of Subjects Previously Enrolled in Immunotherapy Studies Utilizing Gene Transfer or other Immunotherapeutic Agents" once off study.

⁷ Chemistries: sodium, potassium, chloride, CO₂, creatinine, glucose, BUN, albumin, calcium, magnesium, phosphorus, alkaline phosphatase, ALT, AST, total bilirubin, direct bilirubin, LD, total protein, total CK, uric acid

⁸ When logistically feasible, pre-treatment and post-treatment samples may be obtained from consenting patients.

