3.5 Criteria for Removal from Protocol Therapy and Off Study Criteria

Prior to documenting removal from study, effort must be made to have all subjects complete a safety visit approximately 3-4 weeks following the last dose of study therapy.

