3.5.1 Criteria for removal from protocol therapy

- Completion of protocol therapy
- Clinical progression of disease based on increased symptoms or immune related response criteria (irRC) to also be implemented for disease progression as described in 6.3.2.
- Grade 3 or greater toxicity attributed to treatment that does not resolve to grade 1 within 21 days from time of scheduled treatment.
- Grade 3 or greater autoimmune disease that threatens vital organs.
- Intercurrent illness or medical circumstances. If at any time the constraints of this protocol are detrimental to the patient's health, the patient may be removed from protocol therapy and reasons for withdrawal will be documented.
- Subject decides to withdraw from the study (In this event, the reasons for withdrawal will be documented)
- Investigator discretion
- Positive pregnancy test

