3.5.2 Off-Study Criteria

Patients will be removed from the study for the following:

- Subjects proceeds to alternative treatments
- Death
- Patient requests to be taken off study. Reasons for withdrawal will be documented.
- Noncompliance with protocol guidelines (patient removed at discretion of Principal Investigator).
- Investigator decides to end the study
- Screen failure

Patients will be offered enrollment in the 04-C-0274 "Follow-Up Study of Subjects Previously Enrolled in Immunotherapy Studies Utilizing Gene Transfer or other Immunotherapeutic Agents" once off study.

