4.1.1 Acceptable Concomitant Medications

All treatments that the investigator considers necessary for a subject's welfare may be administered at the discretion of the investigator in keeping with the community standards of medical care. All concomitant medication will be recorded on the case report form (CRF) including all prescription, over-the-counter (OTC), herbal supplements, and IV medications and fluids. If changes occur during the trial period, documentation of drug dosage, frequency, route, and date may also be included on the CRF.

All concomitant medications received within 28 days before the first dose of trial treatment and 30 days after the last dose of trial treatment should be recorded. Concomitant medications administered after 30 days after the last dose of trial treatment should be recorded for SAEs as defined in Section **7.1.5**.

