7.3.3 Reporting of Pregnancy and Lactation

Although pregnancy and lactation are not considered adverse events, it is the responsibility of investigators or their designees to report any pregnancy or lactation in a subject (spontaneously reported to them) that occurs during the trial.

Pregnancies and lactations that occur after the consent form is signed but before treatment allocation/randomization must be reported by the investigator if they cause the subject to be excluded from the trial, or are the result of a protocol-specified intervention, including but not limited to washout or discontinuation of usual therapy, diet, placebo treatment or a procedure.

Pregnancies and lactations that occur from the time of treatment allocation/randomization through 120 days following cessation of manufacturer's product, or 30 days following cessation of treatment if the subject initiates new anticancer therapy, whichever is earlier, must be reported by the investigator. All reported pregnancies must be followed to the completion/termination of

the pregnancy. Pregnancy outcomes of spontaneous abortion, missed abortion, benign hydatidiform mole, blighted ovum, fetal death, intrauterine death, miscarriage and stillbirth must be reported as serious events (Important Medical Events). If the pregnancy continues to term, the outcome (health of infant) must also be reported.

Such events must be reported within 2 working days of receipt to Merck Global Safety. (Attn: Worldwide Product Safety; [contact]).

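### New adverse events must be collected for only 30 days after removal from treatment, or less if the patient goes off study, although the protocol expects immune events months after the last dose

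*Combined protocol and SAP*

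**What the plan says.** Section 6.1 (Data Collection) gives the follow-up rule: "Patients will be followed for adverse events for at least 30 days after removal from study treatment or until off-study, whichever comes first". The same paragraph has events that are already open followed until they return to baseline or stabilise.

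Section 3.3.1 (Dose Modifications) says of immune events: "These adverse events may occur shortly after the first dose or several months after the last dose of treatment".

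Two places describe contact after treatment. Section 3.5 asks for effort, before removal from study is documented, to have every subject "complete a safety visit approximately 3-4 weeks following the last dose of study therapy". Footnote 6 of the Study Calendar (3.4) has the "Post-Therapy Assessment done 3 weeks after last treatment when logistically feasible", extendable to 4 weeks.

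Section 3.5.2 lists "Subjects proceeds to alternative treatments" among the reasons for going off study. Progression is listed in 3.5.1 instead, as a reason to stop protocol therapy: "Clinical progression of disease based on increased symptoms or immune related response criteria (irRC").

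Section 4.1.1 limits medication records to 30 days after the last dose, with one extension: "Concomitant medications administered after 30 days after the last dose of trial treatment should be recorded for SAEs". Section 7.3.1 asks for all serious adverse events to be sent to the manufacturer and states no end date. Patients who go off study are offered a separate follow-up study, 04-C-0274.

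**The concern.** The 6.1 sentence joins a minimum to a cut-off. A minimum cannot come first, so the only workable reading is that the duty ends at the earlier of 30 days after removal from treatment and going off study. On that reading there is no floor, because some off-study reasons can arise at any time.

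Safety is a secondary objective (1.1.2). Section 10.5 describes minimally symptomatic patients who would generally be monitored rather than treated, and argues that immune events are likely to be manageable. With 30 evaluable patients and an accrual ceiling of 32, a few uncollected late events could change the safety description. Observation time would also depend on what happens to the patient, because it is cut when another therapy starts. A crude proportion with late immune events would then mix patients watched for different lengths of time.

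**Working it through.** The plan gives no figure for this point, so there is none to reproduce. The check compares the passages and then works out the window.

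**Side by side**

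- Expected onset of immune events: up to months after the last dose (3.3.1).
- Required collection of new events: the earlier of 30 days after removal and off-study (6.1).
- Scheduled safety visit: weeks 3 to 4, that is days 21 to 28 after the last dose (3.4, 3.5).
- Later scheduled contact whose purpose is to find adverse events: none stated.

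**Window counted from the last dose**

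Required end = min(R + 30, S), where R is the day of removal from treatment and S is the off-study day, both counted from the last dose.

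- Removal on the day of the last dose, still on study: 0 + 30 = day 30.
- Removal decided at the next three-weekly visit, still on study: 21 + 30 = day 51.
- Removal after a 12-week hold (Table 4), still on study: 84 + 30 = day 114.
- Off study on day S before R + 30: the requirement ends on day S. With S = 14, taken only as an illustration, it ends on day 14 under the wording of 6.1.

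**Illustration of what a window captures**

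The documents give no onset distribution. Assume that, among immune events starting after the last dose, time to onset is exponential with median m days. The share starting within w days is 1 − 0.5^(w/m). For m = 90 and w = 30 this is 1 − 0.5^(30/90) = 0.206.

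| Assumed median onset | 14 days | 30 days | 51 days | 114 days | 120 days |
|---|---|---|---|---|---|
| 30 days | 0.276 | 0.500 | 0.692 | 0.928 | 0.938 |
| 60 days | 0.149 | 0.293 | 0.445 | 0.732 | 0.750 |
| 90 days | 0.102 | 0.206 | 0.325 | 0.584 | 0.603 |
| 120 days | 0.078 | 0.159 | 0.255 | 0.482 | 0.500 |

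Under these assumptions a 30-day window holds between 16% and 50% of such onsets, and a 120-day window between 50% and 94%. The medians are assumptions chosen to span the protocol's description; they are not trial data.

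**The case against.** The strongest reply is that the plan collects more than 6.1 suggests when read alone.

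- The 30 days is worded as a minimum and runs from removal, not from the last dose.
- Section 3.5 wants the 3 to 4 week visit attempted before off-study status is documented.
- Serious events have an open-ended reporting route (7.3.1), and 4.1.1 anticipates them after day 30.
- Open events are followed until they settle, and patients who remain on study have imaging and EKG every 3 months.
- The follow-up study is offered.
- Section 8 contains no formal safety analysis, so no decision rule changes.

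All of this is correct, and it limits the point. It does not remove it. Reporting on receipt does not find events, scans and EKGs are not adverse-event contacts, the follow-up study is voluntary and its safety content is not described, and the 3.5 visit is an effort requirement that falls by day 28.

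A reader might infer several stronger statements that the documents do not support:

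- That follow-up is at most 30 days, or 30/120 = 25% of a risk period. This mixes two clocks: 51/120 is 43% and 114/120 is 95%. The 120 days is also never called the immune risk period. It concerns contraception (10.7) and pregnancy reporting (7.3.3, "Pregnancies and lactations that occur from the time of treatment allocation/randomization through 120 days following cessation of" the product), and the latter shortens to 30 days if new anticancer therapy starts.
- That a patient who switches on, say, day 10 is closed to follow-up that day. Section 3.5 still asks that the later visit be attempted.
- That progressing patients are followed least. Progression ends therapy, not study participation; only those who start another treatment are affected.
- That 84 − 30 = 54 days of steroid taper go unrecorded. During a hold nobody yet knows which dose is the last, so medication recording continues.

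**Conclusion.** The point holds in limited form. New adverse events must be collected only until 30 days after removal from treatment, or less if the patient goes off study first, while 3.3.1 expects onset months after the last dose. Late-onset immune events are therefore not systematically collected, which is weaker than saying that they are missed. Required observation time is shortest in patients who switch therapy quickly.

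The size cannot be fixed from the documents, because neither the number and timing of switches nor the onset distribution is given. The window arithmetic (days 30, 51 and 114 while on study) rests on stated intervals and on when removal is decided; the capture shares rest on an assumed exponential onset. The primary endpoint and the cohort decision rule are unaffected. The change is worth making because it is cheap and bears on a stated objective.

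**What to change.** Reword 6.1 so that all adverse events are collected for at least 30 days after the last dose, regardless of off-study status or new therapy, except after death or withdrawal of consent to follow-up. Where removal is decided after the last dose, keep the present 30 days from removal as well, so that nobody's follow-up becomes shorter.

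Collect serious and suspected immune-mediated events, with the steroids given for them, over a longer stated window that fits 3.3.1. One option is 120 days, a length the protocol already uses for pregnancy and contraception; the choice for immune events should be justified in its own right. Schedule one telephone contact near the end of that window, and flag events that start after new anticancer therapy.

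In 3.5.2, state that starting another treatment does not end this safety follow-up. In 4.1.1, extend medication recording after day 30 to steroids given for suspected immune-mediated events. In the safety report, give the observation time after the last dose alongside any count of late events.

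The cost is a protocol amendment and about 32 calls, one per patient at the accrual ceiling. Some late events will be confounded by later therapy; the flag lets them be shown separately but does not resolve their cause.
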